In systemic medications, bioequivalence studies are required to demonstrate the interchangeability of the generic by the innovator; Generally, these consist of the determination of the plasma concentration of the drug. Nevertheless, this is not possible for drugs in ophthalmic formulations, due to the low concentrations available in plasma after topical application.

In Mexico, and other countries, generic ophthalmic drugs can obtain their registration fulfilling certain specifications in their formulation and characterization, not requiring clinical studies.

In general, published scientific data supporting the equivalence of a generic ophthalmic and the innovative are scarce.

5.4 Justification.

Travatan® developed by Alcon Laboratories, Inc. was the first 0.004% travoprost formulation commercially available in Mexico and other countries in the world. Since 2001, Travatan® has registered with COFEPRIS. Currently there are generic options in Mexico, which do not have their own clinical studies, supported only by the information and publications of the innovator.

PRO-179 is a formulation of travoprost 0.004%, elaborated by Sophia Laboratories, S.A. of C.V., which is not yet commercially available but has registration with COFEPRIS under the distinctive name of Bristrio®. Although it is a generic product, which does not differ in the concentration of the active principle in relation to the innovative Travatan®, it is desired to document its safety and tolerability profile in a phase I study.

5.5 Objectives and hypothesis.

5.5.1 General objective.

- To evaluate the safety and tolerability of the ophthalmic solution PRO-179 on the ocular surface.

5.5.1.1 Specific objectives.

- Compare the safety of the ophthalmic solution PRO-179 with Travatan® by means of the incidence of adverse events during the study.
- To compare the tolerability of the ophthalmic solution PRO-179 with Travatan® by means of the ICO score.

5.5.2 Secondary objectives.

- Compare the safety of PRO-179 with Travatan® through changes in visual ability during visits.
- Compare the safety of PRO-179 with Travatan® through changes in corneal and conjunctival stains with lysine green during visits.
- Compare the safety of PRO-179 with Travatan® through changes in corneal and conjunctival stains with fluorescein during visits.
- Compare the safety of PRO-179 with Travatan® through changes in conjunctival hyperemia during visits.

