- Have started the use of hormonal contraceptives or IUD, 30 days prior to inclusion in the present study.
- Having a history of any chronic-degenerative disease.
- Present inflammatory or infectious disease, active at the time of study entry.
- Present unresolved injuries or traumas at the time of study entry.
- Having a history of any type of eye surgery.
- Have undergone surgical procedures, not ophthalmological, in the last 3 months.

6.2.1.3 Elimination criteria.

- Withdrawal of the consent letter under information.
- Presentation of a serious adverse event related or not to the investigational product, which has criteria of the PI and / or the sponsor could affect the ability of the patient to continue with the study procedures safely.
- No tolerability or hypersensitivity to any of the compounds used during the tests (fluorescein, green lysine, tetracaine)
- No tolerability or hypersensitivity to any of the investigational drugs.

6.2.2 Lifestyle considerations.

For the study it is necessary that the participants modify the following activities of their lifestyle:

- Abstain from alcohol consumption, from entering the study to taking laboratory tests of the final visit.
- Refrain from tobacco use.
- Refrain from the use of electronic vaporizers.
- Avoid submerging in water without eye protection (goggles-protective glasses).
- Avoid direct exposure to fans (including air conditioning vents) during activities that involve sight. 24 hours before your review visits.
- Do not modify your sleep-wake cycle with which you enter the study.

6.2.3 Scrutiny failures.

A failure to scrutinize is defined as those participants who agree to participate in the study, granting their consent, but who are not assigned to any intervention, that is, they do not enter the study. It is necessary that the following information of the inclusion faults be reported minimally:

- Demographic data.
- Details of the scrutiny failure (specify if it is due to the eligibility criteria, to which, or some other reason for the failure).
- Presence of serious adverse events during the scrutiny.

The above is necessary to comply with the CONSORT (Consolidated Standards of Reporting Trials) guidelines for the publication of results or to answer possible questions from the regulatory authorities.

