- Intra-group analysis: will be determined by the Wilcoxon rank test, for quantitative variables [65]
- Inter-group analysis: will be determined by the Mann-Whitney U test Kruskal-Wallis. This non-parametric test will be used to test whether a group of data comes from the same

population. Intuitively, it is identical to the ANOVA with the data replaced by categories using the student's t statistic.

The level of difference to consider significance will be an alpha of 0.05 or less.

The result of nominal and ordinal qualitative variables will be presented in frequencies, proportions and percentages, see table 3 (section 6.4.3).

The statistical analysis to identify significant differences of the qualitative variables will be done creating 2x2 contingency tables and it will be done in the following way:

- Intra-group difference: McNemar test [66]. Which is applied to 2×2 contingency tables with a dichotomous trait, with pairs of matched subjects, to determine if the marginal frequencies of row and column are equal (marginal homogeneity).
- Inter-group difference: Pearson's χ^2 test (or Fisher's exact).

The level of difference to consider significance will be an alpha of 0.05 or less.

For the reporting of adverse events all eyes of those participants who were randomly assigned to an intervention group after the baseline visit will be considered. The results will be expressed in number of cases (eyes).

The final report of the results will be shown in tables or graphs, as appropriate.

It will be considered that the investigational drug is safe and tolerable when there are no clinical and statistical differences in all the variables of primary outcome, with respect to its comparators.

Those subjects who comply with an adherence greater than 60% will be included in the statistical analysis to meet the objective of the study, taken from the subject's diary. It was considered that from the minimum dose necessary to obtain a pharmacological effect (hypotensive / 1 application per day) and the presence of adverse events (exposure) is sufficient to meet the overall design objective, according to the pharmacological characteristics of the IP.

8.3.2 Additional analyzes.

No additional analyzes are contemplated to those previously described. Nevertheless, these may be performed if during the conduction of the study it is required to analyze specific safety aspects of any intervention, maintaining the blinding until the end of the study.

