Record the withdrawal or maintenance of the medication, IP or investigational medication, as appropriate. Indicate if the adverse event disappears when the IP or investigational medication or suspicious medication is removed (to provoke the event). Also indicate if a dose adjustment is made, if the event changes in terms of intensity or seriousness, persistence of the reaction. It is important to indicate that in those patients who are exposed again to the IP, investigational medication or medication, which had previously been suspended, if the adverse reaction or adverse event reappears.

Regarding concomitant pharmacotherapy. Indicate the generic name, the dose, the route of administration, start and end dates of its use, as well as the reason for the prescription regardless if it is consistent with the information to prescribe or technical data sheet or is used outside the regulations or of what the local, national or international regulatory entity has authorized.

Concerning the relevant clinical antecedents. The analysis of the adverse event considers the information previously reported, notwithstanding the clinical context in which this harmful phenomenon occurs in the participants of the clinical research protocol, it is of special interest, so that information about the previous conditions, phenomena of hypersensitivity or allergy, previous surgical procedures, laboratory analysis or cabinet examinations that have been practiced on the participant, etc., that the investigator deems fit to mention may do so. In case to have enough space in the case report format, you can complete the information in your clinical note in the clinical file.

9.2.1.2 Monitoring of adverse events.

The PI will provide the attention and guidance of the EA that the participant presents until the outcome of the same, according to what is referred to the following section.

9.2.1.3 Procedures for a serious adverse event.

The process of attention of the adverse event considers the following stages:

[figure not shown]

Figure 5. Attention to the adverse event.

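### Stopping because the product is not tolerated is counted in no outcome, and such subjects can drop out of the ICO comparison, leaving adverse-event incidence as a weak safeguard

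*Combined protocol and SAP*

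**What the plan says.** Among the elimination criteria, section 6.2.1.3 lists "No tolerability or hypersensitivity to any of the investigational drugs". Section 5.5.1.1 sets the tolerability objective as "To compare the tolerability of the ophthalmic solution PRO-179 with Travatan® by means of the ICO score" and the safety objective as "Compare the safety of the ophthalmic solution PRO-179 with Travatan® by means of the incidence of adverse events during the study". Section 6.4.1.2 names ICO as the sole primary tolerability variable, and the synopsis times it at day 11. Nothing in 6.4.1, 6.4.2 or Table 3 counts eliminations or stops for intolerance.

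Section 8.3.1 joins the two primary variables in one verdict. The drug is "safe and tolerable when there are no clinical and statistical differences in all the variables of primary outcome, with respect to its comparators". For AE reporting, "all eyes of those participants who were randomly assigned to an intervention group after the baseline visit will be considered". For the analysis that serves the objective, "Those subjects who comply with an adherence greater than 60% will be included in the statistical analysis to meet the objective of the study". Section 8.3.3 describes an intention-to-treat analysis but admits only participants who completed Visit 1.

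Section 6.5.1.6 gives a subject who leaves early an unscheduled visit that stands in for the final visit, and 6.5.1.4 includes ICO among the final-visit procedures. If the subject refuses, the last visit made is taken as final. Visit 1 has no ICO (6.4.4, 6.5.1.3). The AE record in 9.2.1.1 asks the site to "Record the withdrawal or maintenance of the medication, IP or investigational medication, as appropriate", and 6.2.4 and 8.1.1 ask for the reason for leaving when no appointment can be arranged.

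The plan does not say how an eliminated subject is analysed.

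**The concern.** A subject who cannot continue the assigned product because of intolerance is the plainest evidence on the trial's tolerability question. The plan treats that event as a disposition reason and then filters the analysis set in ways that tend to remove the same subjects from the one tolerability variable. To that extent the ICO comparison is made among those who tolerated the product.

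This pushes the result in one direction. The verdict rests on finding no difference, so losing the worst responders from either arm moves the trial towards declaring the product tolerable. AE incidence is the only remaining primary variable that could show the imbalance, and in it an intolerance withdrawal weighs no more than a mild transient event.

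**Working it through.** The plan gives no figure for stops due to intolerance, so there is none to reproduce. The inputs from the documents are 12 subjects per arm (6.6), 10 nightly doses in both eyes (6.3), Visit 1 on day 5 ± 1 (6.4.4), the adherence rule (6.3.2.1, 8.3.1), background rates of 41.9% for ocular AEs and 12.9% for hyperemia with travoprost (6.6.1), and 27% as the lower end of the hyperemia range in 5.2.3. The assumptions are 4 or 5 of 12 intolerant subjects on one arm and none on the other, and equal ICO distributions otherwise.

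**Step 1: who fails the adherence filter.** Final adherence is the average of the per-visit values, each 100 × registered / indicated. With about 4 doses before Visit 1 and 6 after, and the denominators kept at the scheduled doses:
- stop after 5 doses: (4/4 + 1/6)/2 = 58.3%, excluded;
- stop after 6 doses: (4/4 + 2/6)/2 = 66.7%, included.

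The Visit 1 window moves the cut. With 3 doses before Visit 1, stopping after 4 or fewer excludes: (3/3 + 1/7)/2 = 57.1%. With 5 before, stopping after 6 or fewer excludes: (5/5 + 1/5)/2 = 60.0%, which is not above 60%. A simple ratio also excludes at 6 (6/10 = 60%). An early stopper therefore leaves the ICO comparison even if ICO was taken at the termination visit. If the indicated doses were instead counted only up to the stop, the subject would pass; the plan does not say which applies.

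**Step 2: effect on the ICO test.** Two-sided Mann-Whitney at 0.05, simulated with normal scores. The documents give no ICO standard deviation, but only ranks matter when stoppers are dropped or ranked worst.

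| Intolerant, of 12 v 0 of 12 | Dropped | Kept, 2 to 3 SD worse | Ranked worst |
|---|---|---|---|
| 4 | about 5% | 15% to 20% | about 21% |
| 5 | about 4% to 5% | 25% to 33% | about 36% |

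**Step 3: the AE route.** Fisher's exact test at 0.05, two-sided. The 4 intolerant subjects are certain to have an AE; all others have one at the background rate. Enumerating the binomial outcomes gives the share of trials in which the test flags the affected arm:

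| Background AE rate, both arms | By subject (12 v 12) | By eye, every AE bilateral (24 v 24) |
|---|---|---|
| 12.9% | 16% | 50% |
| 27% | 10% | 39% |
| 41.9% | 7% | 30% |

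The by-eye column treats the two eyes of a subject as independent. With no true difference, the same by-eye test rejects in about 8%, 12% and 15% of trials at these three rates, so part of its apparent sensitivity is false-positive rate. With no background AEs at all, 8/24 v 0/24 eyes gives p = 0.004.

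**Step 4: counting the stops directly.** By subject, Fisher p = 0.217 for 3/12 v 0/12, 0.093 for 4/12 v 0/12 and 0.037 for 5/12 v 0/12. The exact 95% interval for 4/12 is 9.9% to 65.1%, and for 0/12 it is 0% to 26.5%. Power of the direct test is 0.16 for true rates of 25% v 0% and 0.37 for 33% v 0%.

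**The case against.** A reader might infer that tolerability is judged on ICO alone, so that a product which drives subjects off treatment would pass unseen. The documents do not support that:
- The 8.3.1 verdict requires no clinical and no statistical difference in all primary variables, and AE incidence is one of them.
- AEs are reported on all randomised eyes, so that report is not conditioned on tolerating the drug.
- The safety call still follows an early termination, and withdrawal of the product, intensity and causal relationship are recorded (9.2.1.1, 9.2.1.3).
- Section 6.2.1.3 does not say that an eliminated subject's data are discarded, and the early-termination visit can supply an ICO.
- Counted in eyes with no background AEs, 4 v 0 bilateral intolerances would fail the rule (p = 0.004).

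All of this stands, and it rules out saying that the trial cannot detect an imbalance. It does not close the gap. The loss comes from the filters in 8.3.1 and 8.3.3, which act even when a termination ICO exists. The AE variable in Table 3 is a count or present/absent, so recorded withdrawal and intensity carry no weight in the verdict. Common travoprost AEs dilute the signal. The plan does not say whether the AE test itself uses all randomised subjects or the adherence-filtered set, and no threshold defines a clinical difference.

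It is also fair that 4 or 5 of 12 is an assumption with no basis in the documents; section 6.2.4 anticipates no retention problems. If nobody stops for intolerance, the point has no numerical effect.

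**Conclusion.** The point holds in this form: stops for intolerance count in no outcome, early ones can fall out of the only tolerability variable, and AE incidence is a real but weak safeguard at 12 per arm. In the 4 v 0 example, dropping the stoppers leaves the ICO test at about its null rate (5%), against about 21% if they are ranked worst. A by-subject AE test flags the imbalance in 7% to 16% of trials; a by-eye test does so in 30% to 50%, but with an inflated false-positive rate.

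These figures assume the stated numbers of intolerant subjects, equal ICO otherwise, adherence measured against scheduled doses, and certain AEs (bilateral in the by-eye count) in the intolerant subjects. The structural finding does not depend on them.

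A direct count is not a powerful test either. The non-significance of 4 v 0 (p = 0.093) should not be read as similarity. This should be corrected, but it does not invalidate the design.

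**What to change.** In 8.3.1 and 8.3.3:
- Exempt subjects who stop for intolerance or hypersensitivity to the assigned product from the adherence and Visit 1 filters, and keep every randomised, dosed subject in the tolerability analysis.
- Report the ICO taken at the early-termination visit where there is one. In the Mann-Whitney comparison, rank all subjects who stopped for intolerance as worst, that is, highest discomfort. Show the plain ICO summary beside it.
- Report the number of such stops by arm, per subject, with exact confidence intervals.
- Have the 8.3.1 verdict consider these stops alongside ICO and AEs, and state that a non-significant difference in them is not evidence of similarity.

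A matching sentence in 5.5.1.1 and 6.4.1.2 would align the objective and the variable. The cost is a few sentences and one table. Withdrawal of the product is already part of the AE record, and the reason for leaving is already asked when a subject cannot be rescheduled. The downside is that the ICO comparison becomes a ranked composite for the few affected subjects. The clinical decision to stop the product stays as it is.

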At the counting stage, the participant number will be assigned consecutively, using 3 consecutive digits. Once the subject has been selected, he will be assigned a number with which he will be identified throughout the study. Said code will be composed of eight numbers in the following order from left to right:

- three digits of the molecule under study according to the denomination by the sponsor.
- two digits corresponding to the research center number.

- three digits of the number consecutive to its inclusion assigned to the research center.

Example:

6.3 Intervention.

The subjects will be divided into two equal groups, to which they will be assigned randomly and blinded to one of the products in research (PI) PRO-179 or Travatan®.

Dosage: 1 drop every 24 hours, at night, in both eyes.

Instructions for administration: instillate a drop in the conjunctival sac, it is recommended to exert gentle traction on the lower eyelid, with the index finger, to expose the cul-de-sac and instillation. Avoid blinking energetically for the next few minutes or closing your eyes in a forced way.

Duration of the intervention: 10 days.

6.3.1 Medications administered.

6.3.1.1 Drug under study.

- Generic name: Travoprost
- Distinctive denomination: Bristrio® (PRO-179)
- Active principles: Travoprost 0.004%.
- Pharmaceutical form: Ophthalmic solution
- Presentation: multi-dose dropper bottle, 2.5 ml.
- Prepared by: Sophia Laboratories, S.A. of C.V.
- Description of the solution: transparent solution, free of visible particles.
- Description of container: White bottle with 5mL capacity, made of low density polyethylene.

Agent	Quantity mg / mL	Function
Travoprost	0.040	Active principle
Hydroxypropylbetacyclodextrins	Not showing	Stabilizer
Mannitol	Not showing	Toning
Boric acid	Not showing	Buffer Agent
Sodium Borate Dehydrated	Not showing	Buffer Agent
Disodium edetate Dihydrate	Not showing	Chelating Agent
Benzalkonium Chloride (1)	Not showing	Conservative
Water for the preparation of Injectables c.b.p.	1.000 mL	Vehicle

Table 2. Quali-quantitative formulation of PRO-179

6.3.1.1 Reference medicine.

- Generic name: Travoprost
- Distinctive denomination: Travatan®
- Active ingredients: Travoprost 0.004%
- Pharmaceutical form: Ophthalmic solution.
- Presentation: multi-dose dropper bottle, 2.5 ml.
- Prepared by: Alcon Laboratories Inc.
- Description of the solution: transparent solution, free of visible particles.
- Consult information to prescribe.

6.3.2 Strategies to improve adherence and procedure to monitor adherence.

1. 1. Direct questioning by the PI about the application of the IP.
2. 2. Delivery of a printed calendar specifying the date of the visit and its activities.
3. 3. Journal of the subject.

6.3.2.1 Procedure to monitor adherence.

For more than four decades, there have been numerous investigations on the proper way to measure and quantify adherence to medications, however none has reached consensus to establish itself as the gold standard, both in cross-sectional and longitudinal studies. [48, 49, 50, 51, 52, 53, 54, 55]

There are different procedures to measure the adherence of pharmacological interventions. The most common procedure includes self-reports, these include: patient interviews, questionnaires and self-monitoring journals. Its strengths are speed, flexibility, low cost and ease of implementation; they have a high degree of specificity for non-adherence, nevertheless, the sensitivity and reliability for adherence is low. [55, 56]

The biochemical measurement of the drug, or its metabolite, is one of the methods that best confirms the use of the drug. Nevertheless, in addition to raising costs and being impractical, it is of little use in the context of ophthalmic applications, since concentrations at the peripheral level could be undetectable; and samples from other tissues imply more invasive methods that would not be advisable. [55]

Medication counting is another way to measure adherence. Classically referred to as "pill counting", in ophthalmology it is translated to the weight of the bottle. This is a simple, economical and non-invasive method. The main disadvantages of this method are: 1. The application of the medication can not be confirmed (it could have been intentionally thrown or instilled out of the eye) and 2. It depends on the subject bringing back the medication. [55, 56]

For the purposes of this study, the evaluation of the adherence will be favored by means of the diary of the subject, and will be carried out in the following way:

$$Ad = (A_r)100/A_i$$

Ad = Adherence

Ar = Registered applications

Ai = Applications indicated for the IP

The final adhesion will be determined by the average of the adherence of each one of the visits. Overall adherence (all subjects) will be determined by the average final adherence of each of the subjects.

6.3.3 6.3.3 Treatments and concomitant medications allowed and prohibited during the study.

The use of concomitant medications by any route of administration during the intervention period will not be allowed. Except those specified for the study procedures and hormonal contraceptives in case of fertile women. The objective of this restriction is to avoid pharmacological interactions that could alter the results of the evaluated variables.

Nor is the use of herbal or naturist products, whose purpose is to modify some physiological function of the subject.

6.3.4 Treatment management.

The IPs will be provided by Sophia Laboratories, S.A. of C.V. It will be the responsibility of the sponsor to select and ensure the logistic methods for the distribution of the medication. They will be labeled and reconciled. The handling of the treatment will be under the responsibility of the researcher or a designated member of his team.

6.3.4.1 *Delivery and reception.*

The delivery will be made through a courier service hired by the sponsor, specifically selected for this purpose, at the address of the research center according to the study plan.

The reception will be exclusively carried out by the non-blind staff of the research team. You must check the good condition of the primary packaging (box). In case it shows alterations or defects in its integrity that from its judgment could have damaged the content should report it to the sponsor. If the package does not show significant defects, it will proceed to open it.

Inside you must locate the acknowledgment document and the logger (data logger) of temperature and humidity. You should check that the registered temperature and humidity comply with the specifications for transport and shelter (see section 6.3.4.2 Storage). Verify the content (PI) with what is reported in the document. In case the document corresponds to the content, it will sign the receipt and send it to the sponsor. Otherwise, notify the sponsor.

6.3.4.2 *Storage.*

Storage and safekeeping is the responsibility of the sponsor and the research center. The medication must be stored in a secure area with restricted access.

The storage temperature should be 2 ° C to 25 ° C.

The research center has the obligation to record, in the designated format, the temperature recorded in the data logger, every day while the protocol is in force and has IPs.

These data will be reviewed by the clinical monitor according to the registration in the data logger.

6.3.4.3 *Return.*

The return will be made by the research center when the sponsor indicates it. Prior to the return, the research center must make a count of the assigned medication and the remaining medication, with the aim of creating an inventory which serves for the final filling of the medication return form.

6.4 Delay variables.

6.4.1 Security variables.

6.4.1.1 Primary outcome variables.

- Incidence of adverse events.

6.4.1.2 Variables of primary outcome of tolerability.

- ICO score.

6.4.1.3 Secondary outcome variables.

- Changes in visual ability.
- Changes in corneal and conjunctival staining with lysine green.
- Changes in corneal and conjunctival staining with fluorescein.
- Changes conjunctival hyperemia.
- Incidence of chemosis.
- Incidence of alterations in the results of laboratory tests.
- Incidence of alterations in the FC.
- Incidence of alterations in the RF.
- Incidence of alterations in the TAS.

6.4.2 Exploratory variables.

- Changes in IOP.

6.4.3 Methods and scales to be used for the measurement of the variables.

Variable	Kind	Unit (Symbol)	Method of measurement	Normal value	Evaluation time	Statistical test
Primary						
Adverse events	Discreet Categorical rating	Number of cases (n) Present/absent	Count Observation	0 Absent	VB, V1, VF y LLS	Mann-Whitney U χ^2 o Fisher's exact
ICO score	Discreet	Points	Questionnaire	NA	VB, VF	Mann-Whitney U
Secondary						
Visual ability	Discreet	Fraction	Snellen Primer	1	VB, V1 y VF	Mann-Whitney U
Corneal and conjunctival staining with fluorescein	Ordinal	Degrees	Direct observation with slit lamp and cobalt blue filter, Oxford scale graduation	0	VB, V1 y VF	χ^2 or Fisher's exact

Variable	Kind	Unit (Symbol)	Method of measurement	Normal value	Evaluation time	Statistical test
Corneal and conjunctival staining with lysamine green	Ordinal	degrees	Direct observation with slit lamp, Oxford scale graduation	0	VB, V1 y VF	χ^2 or Fisher's exact
Conjunctival hyperemia	Ordinal	Normal / Very Light / Mild / Moderate / Severe	Direct observation. Classification of Efron.	Normal	VB, V1 y VF	χ^2 or Fisher's exact
Chemosis	Categorical rating	Present / absent		Absent	VB, V1 y VF	χ^2 or Fisher's exact
FC	Discreet	eats per minute (l / m)	Auscultation with stethoscope	60 to 100	VB, V1 y VF	Mann-Whitney U
FR	Discreet	Breaths per minute (r / m)	Auscultation with stethoscope	12 to 24	VB, V1 y VF	Mann-Whitney U
TAS	Discreet	Millimeters of mercury (mmHg)	Measurement with sphygmomanometer	90-120/ 60-80	VB, V1 y VF	Mann-Whitney U
Erythrocytes	Continuous	Thousands per microliter (Mil / dL)	Laboratory analysis	4.0- 6.3	VB y VF	Mann-Whitney U
Hemoglobin	Continuous	Grams over deciliter (g / dL)	Laboratory analysis	11.0-16.0	VB y VF	Mann-Whitney U
Hematocrit	Continuous	Percentaje (%)	Laboratory analysis	36-51	VB y VF	Mann-Whitney U
VGM	Continuous	Femto liters (fL)	Laboratory analysis	80-97	VB y VF	Mann-Whitney U
HCM	Continuous	Picograms (pg)	Laboratory analysis	25-32	VB y VF	Mann-Whitney U
Leukocytes	Continuous	Thousands per liter units (Mil / uL)	Laboratory analysis	4.0-11.0	VB y VF	Mann-Whitney U
Platelets	Continuous	Thousands per liter units (Mil / uL)	Laboratory analysis	150-400	VB y VF	Mann-Whitney U
Glucose	Continuous	Milligrams over deciliter (mg / dL)	Laboratory analysis	70-100	VB y VF	Mann-Whitney U
Urea	Continuous	Milligrams over deciliter (mg / dL)	Laboratory analysis	10-50	VB y VF	Mann-Whitney U

Variable	Kind	Unit (Symbol)	Method of measurement	Normal value	Evaluation time	Statistical test
Creatinine	Continuous	Milligrams over deciliter (mg / dL)	Laboratory analysis	0.6-1.1	VB y VF	Mann-Whitney U
Glutamic pyruvic transaminase	Continuous	Units over liter (U / L)	Laboratory analysis	0-31	VB y VF	Mann-Whitney U
Oxalacetic glutamic transaminase	Continuous	Units over liter (U / L)	Laboratory analysis	0-32	VB y VF	Mann-Whitney U
Total bilirubin	Continuous	Milligrams over deciliter (mg / dL)	Laboratory analysis	0-1.1	VB y VF	Mann-Whitney U
Direct bilirubin	Continuous	Milligrams over deciliter (mg / dL)	Laboratory analysis	0.0-0.3	VB y VF	Mann-Whitney U
Indirect Bilirubin	Continuous	Milligrams over deciliter (mg / dL)	Laboratory analysis	0.0-0.8	VB y VF	Mann-Whitney U
Exploratoria						
Presión intraocular	Continuous	Millimeters of mercury (mmHg)	Goldmann Tonometry	10 to 21	VB, V1 y VF	Mann-Whitney U

Table 3. Table of operational definitions of variables.

The following describes the methods and scales that will be used to measure the variables, which are in strict alphabetical order:

6.4.3.1 Visual capacity.

Visual acuity (VA) is a test of visual function. Spatial visual acuity is the ability to distinguish separate elements of an object and identify them as a whole. It is quantified as the minimum separation angle (located at the nodal point of the eye) between two objects that allows perceiving them as separate objects.

The Snellen notation is described as the distance at which the test is performed, divided by the distance at which the letter is vertically equivalent to 5 arc minutes. Thus, at 6 meters a letter 6/6 (20/20) equals 5 minutes of arc, a letter 6/12 (20/40) equals 10 minutes, and a letter 6/60 (20/200) equals 50 minutes. The Snellen fraction can also be expressed as a decimal (ie 20/20 = 1 and 20/40 = 0.5). [57]

The VA will be evaluated basally, without refractive correction with the Snellen chart. Which will be located in a place with adequate lighting, natural or artificial and at a distance of 3m from the subject to be evaluated. The visual acuity of each eye will be taken, starting with a right eye (DO) asking the subject to keep both eyes open and using an occluder to cover the left eye (OS); the subject will read aloud the lines that the evaluator points out, the line of smaller letters that he reaches to see

will be annotated by the fractional evaluator as the DO of the DO in the clinical file. Proceed to the OS with the same method.

Subsequently the best refractive correction of the subject will be made and the examination will be repeated using the obtained refraction. This result will be reported as CV, it will be written in fraction in the clinical file and in the CRF, in addition in the CRF it will be written in decimal. By definition, the CV can not be inferior to the AV.

6.4.3.2 Comprehensive ophthalmologic evaluation.

It refers to the ophthalmological exploration of eyelids and appendages, anterior segment and posterior segment that is performed in a routine ophthalmologic review, whose procedures are not specifically included in the study variables. This evaluation has the purpose of identifying unexpected events. The evaluation of the posterior segment will be carried out under drug mydriasis (Tropicamide 0.8% / Phenylephrine 5%), in the slit lamp with an aerial loupe (at the choice of the IP). An integral assessment of the fundus (including optic disc, posterior pole and periphery) will be performed in search of abnormalities that alter the result of the study. The result of the assessment will be recorded in the clinical file. In the CRF it will be registered as normal, abnormal or abnormality that does not affect.

6.4.3.3 Eye comfort index.

It is a questionnaire designed to measure the irritation of the ocular surface with Rasch analysis to produce estimates on a linear scale of intervals (ratings: 0-100). Similar to the index for ocular surface diseases, the ocular comfort index (ICO) evaluates symptoms. The ICO contains items that focus on the discomfort associated with alterations of the ocular surface. Each of these questions has two parts, which inquire separately the frequency and severity of the symptoms. [58] See annex Eye comfort index.

The evaluator will deliver the questionnaire to the subject and allow the subject to answer it calmly without any pressure and / or coercion, will only assist him if he has difficulty understanding any of the questions.

6.4.3.4 Integrity of ocular surface:

This will be done by means of biomicroscopy using the slit lamp of the research center. A full assessment of the previous segment will be made, which will be recorded in the clinical file. The lighting techniques used will be at the discretion of the PI.

The variables that will be registered in this protocol are:

- *Conjunctival hyperemia.*
It is defined as the simplest reaction of the conjunctiva to a stimulus, a red appearance secondary to the vasodilation of the conjunctival vessels of variable intensity. He will graduate using the Efron scale. [59] See annex Efron's scale for conjunctival hyperemia.
- *Chemosis.*
It is defined as conjunctival edema, the result of an inflammatory reaction. It is qualified as present or absent. The assessor will use a narrow beam of light at 60 ° and will measure if the conjunctiva separates from the sclera by $\geq 1/3$ of the total palpebral opening or if it exceeds the gray line. [60]

6.4.3.4.1 Stains.

- *Staining with lysine green.*

A drop of topical anesthetic will be instilled in the conjunctival cul-de-sac, then a drop of saline solution will be applied to the tip of the green lysine strip and it will be allowed to slide

towards the bottom of the sac. It is essential to quickly evaluate the staining, in sequence, first in the OD and then the OS, so that the observed patterns are equally bright. [61] See annex Scale of Oxford.

- *Fluorescein staining.*

A drop of topical anesthetic will be instilled in the conjunctival cul-de-sac, then a second drop will be applied to the tip of the fluorescein strip and it will be allowed to slide towards the bottom of the sac. It is essential to quickly evaluate the staining, in sequence, first in the OD and then the OS, so that the observed patterns are equally bright. This valuation will be done with the cobalt blue filter. [61] See annex Scale of Oxford.

6.4.3.5 Presence of adverse events.

The management of the EAs will be done according to what is described in the Adverse Events section.

The PI will register in the corresponding section of the CRF the EAs that come to present the subjects of the study in addition to referring it in the clinical file.

6.4.3.6 Intraocular pressure.

Tonometry is the objective measure of IOP, based primarily on the force required to flatten the cornea or the degree of corneal indentation produced by a fixed force. Goldman's tonometry is based on the Imbert-Fick principle. [57] The tonometry will be performed, after instillation of a drop of topical anesthetic (tetracaine 0.5%), with fluorescein and the use of the cobalt blue filter (after evaluation of the corneal surface staining). There will be 3 shots, which will be recorded in the clinical file and the average will be registered in the CRF.

6.4.3.7 Vital signs.

The vital signs to be evaluated (FC, FR and TAS) can be measured by an assistant duly indicated in the organization of the center and the delegation of responsibilities, the technique to be used for the FC and FR will be with the count of repetitions in one minute by direct auscultation with stethoscope.

The SBP should be measured with 5 minutes of previous rest, in the left arm. The instrument can be manual or automatic according to the PI. It is necessary that all measurements are equal in circumstances. The PI will register in the note and the CRF.

6.4.3.8 Laboratory tests.

